7.1.1. ECG Changes

A participant who meets either of the bulleted criteria below based on the average of triplicate ECG readings will be withdrawn from the study intervention.

- QTcF >500 msec.
- Change from baseline: QTcF >60 msec.

If a clinically significant finding is identified (including, but not limited to, changes from baseline in QTcF after enrollment), the investigator or qualified designee will determine if the participant can continue in the study and if any change in participant management is needed. This review of the ECG printed at the time of collection must be documented. Any new clinically relevant finding should be reported as an AE.

7.1.2. Potential Cases of Acute Kidney Injury

Abnormal values in SCr and SCysC concurrent with presence or absence of increase in BUN that meet the criteria below, in the absence of other causes of kidney injury, are considered potential cases of acute kidney injury and should be considered important medical events.

An increase of ≥ 0.3 mg/dL (or ≥ 26.5 μ mol/L) in SCr level and increase of $\geq 30\%$ in SCysC level relative to the participant's own baseline measurement should trigger another assessment of SCr and SCysC as soon as practically feasible, preferably ***within 48 hours from awareness***.

If the second SCr assessment (after the first observations of ≥ 0.3 mg/dL [or ≥ 26.5 $\mu\text{mol/L}$] in SCr increase relative to the participant's own baseline measurement) is ≥ 0.4 mg/dL (or ≥ 35.4 $\mu\text{mol/L}$), **and** if the second SCysC assessment (after the first observation of $\geq 30\%$ increase relative to the participant's baseline measurement) remains increased by $\geq 30\%$, then further dosing of study intervention should be withheld. The participant should continue all safety assessments and adequate, immediate, diagnostic, and supportive measures taken to correct apparent acute kidney injury.

If a participant demonstrates concomitant SCr-based **and** SCysC-based eGFR decline of $\geq 30\%$ compared to the participants' baseline concomitant SCr-based **and** SCysC-based eGFR, then the participant should not be further dosed and adequate, immediate, supportive measures including **urgent evaluation by a nephrologist (preferably within 24 hours) with appropriate management** and treatment as clinically indicated. Safety assessments should be repeated weekly or as indicated by the nephrologist until the renal parameters are deemed to be stable by the nephrologist and/or PI.

If the participant cannot be seen by a nephrologist within 24 hours (as described above), then the participant should be sent to a local emergency room for evaluation and treatment as clinically indicated.

Participants should return to the investigator site and be evaluated as soon as possible, ***preferably within 48 hours*** from awareness of the second assessment confirming abnormal eGFR result (ie, $\geq 30\%$ decline in concomitant SCr-based **and** SCysC-based eGFR). This evaluation may include laboratory tests, detailed history, and physical assessment. In addition to repeating SCr and SCysC, laboratory tests should include serum BUN, serum creatine kinase, and serum electrolytes (including at a minimum potassium, sodium, phosphate/phosphorus, and calcium), in addition to urinary dipstick, urine microscopic examination, urinary indices, as well as UACR and UPCR. All cases confirmed on repeat testing as meeting the laboratory criteria for acute kidney injury (ie, increase in SCr **and** increase in SCysC), with no other cause(s) of laboratory abnormalities identified, should be considered potential cases of drug-induced kidney injury irrespective of availability of all the results of the investigations performed to determine etiology of the abnormal SCr and/or SCysC. If ≥ 2 healthy participants in a **given** dose group (in each of the 3 Parts of the study, ***separately***) are noted to have 2 **consecutive** decreases from baseline in eGFR of $\geq 30\%$, based on concomitant SCr-based **and** SCysC-based eGFR, then an assessment of whether the finding may be considered an adverse drug reaction should be undertaken.

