Primary	To characterize the effect of a high-fat/high-caloric meal , compared to following an overnight fast, on plasma PK profile of PF-07202954 following administration of a single oral dose to healthy, adults.	PK parameters ^a derived from plasma PF-07202954 concentration: 
C_{max}, T_{max}, AUC_{last}, and AUC_{inf}, as data permit.
Secondary	To evaluate safety and tolerability of a single , oral, dose of PF-07202954 administered with a high-fat/high-caloric meal compared to following an overnight fast.	Following assessments over ≥ 5 days of each Period and up to Day 30 ± 2 days post last dose of study intervention – 
AEs;Clinical laboratory tests;Vital signs (including BP and pulse rate);Cardiac conduction intervals via 12-lead ECG.

a. For a complete definition of all PK parameters refer to [Table 8](#) and [Table 9](#).

NOTE: For all non-PK related endpoints, **baseline is defined** as the time-matched data obtained while on placebo [Part 1], 0H assessment on Day 1 or 0-12H or 0-24H assessment prior to 1st dose [Part 2], **or** 0H assessment on Day 1 in **each Period** [Part 3], unless otherwise specified in the SAP.

CCI

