Given the current study is the first time PF-07202954 will be administered to humans, an escalating single oral dose design is planned with careful assessment and ongoing review of safety data and PK of PF-07202954. Part 1 is designed as a randomized, dose -escalating, cross-over, interleaving, placebo-controlled, 2-cohort, study with dosing of study intervention (PF-07202954/placebo) planned following ≥ 10 hours overnight fast, at approximately 8:00AM (± 2 hours) to occur **with** standard morning meal provided ~ 30 mins

prior to dosing at 0H. By design, at each dose level, 6 participants are planned to receive PF-07202954 and 2 participants are planned to receive placebo with all participants at the end of Part 1 having received 1 dose of placebo and up to 3 *unique* doses of PF-07202954. The rationale for selection of the starting (ie, first) dose level in Part 1 is outlined in [Section 4.3.3](#). In addition, the highest anticipated steady-state AUC₂₄ and C_{max} for PF-07202954 in Part 1 will *not* exceed the pre-identified stopping exposure limit determined based on nonclinical toxicity study (refer to [Section 6.6.1](#)) *nor* exceed the highest feasible total daily dose of 2000 mg.

The design of Part 1 permits both a within and between participant assessment of safety/tolerability and dose-response for PK and exploration of effect on plasma PCSK9. Furthermore, to permit an unbiased assessment of safety, the administration of active versus placebo in each Period will be double-blinded to both site staff (except those involved in preparation of doses) as well as the participants. However, to permit real-time review of the safety and PK data, the sponsor will be unblinded, although measures to limit degree of unblinding will be exercised – refer to [Section 9.5](#) for details. In light of the findings in the 6 week toxicity studies in rats and monkeys, the safety assessments envisioned in this study administrating investigational product for the first time to humans are outlined in [Section 8.2](#).

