6.3. Measures to Minimize Bias: Randomization and Blinding

6.3.1. Allocation to Study Intervention

The investigator will assign participant numbers to the participants as they are screened for the study. Pfizer will provide a randomization schedule to the investigator and, in accordance with the randomization numbers, the participant will receive the study treatment regimen assigned to the corresponding randomization number.

Participants will be randomly assigned to receive study intervention from a central randomization scheme. ***In Part 1 and Part 2***, investigators will remain blinded to each participant's assigned study intervention throughout the course of the study. In order to maintain this blind, an otherwise uninvolved third party (for example, a pharmacist) will be responsible for the preparation and dispensing of all study intervention according to the randomization schedule and assigned treatment for the individual participant.

For Part 3, the investigator's knowledge of the treatment should not influence the decision to enroll a particular participant or affect the order in which participants are enrolled.

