8.2.2. Vital Signs

In this study, assessment of vital signs (including BP and pulse rate) will occur at the nominal timepoints specified in the [SoA-Table A](#), [SoA-Table B](#), [SoA-Table C](#), and [SoA-Table D](#) per the following specifications:

- **Single, supine BP and pulse rate** will be measured with the participant's arm supported at the level of the heart, and recorded to the nearest mm Hg after **≥5 minute** of rest;
- The same arm (preferably the dominant arm) will be used throughout the study;

- Participants should be instructed *not* to speak during measurements.

The same properly sized and calibrated BP cuff will be used to measure BP each time. The use of an automated device for measuring BP and pulse rate is acceptable; however, when done manually, pulse rate will be measured in the brachial/radial artery for **at least 30 seconds**. When the timing of these measurements coincides with a blood collection, BP and pulse rate should be obtained prior to the nominal time of the blood collection.

Additional collection times, or changes to collection times, of BP and pulse rate will be permitted, as necessary, to ensure appropriate collection of safety data.

8.2.3. 12-lead ECGs

Standard 12-lead ECGs utilizing limb leads (with a 10-second rhythm strip) should be collected at times specified in [SoA-Table A](#), [SoA-Table B](#), [SoA-Table C](#), and [SoA-Table D](#) using an ECG machine that automatically calculates the HR and measures PR, QT, and QTcF intervals and QRS complex. Alternative lead placement methodology using torso leads (eg, Mason-Likar) is not recommended given the potential risk of discrepancies with ECGs acquired using standard limb lead placement. All scheduled ECGs should be performed after the participant has rested quietly for **≥10 minutes** in a *supine position*.

In Part 1, during conduct of the study: *Triplet* 12-lead ECGs will be obtained approximately 2 to 4 minutes apart; the average of the triplicate ECG measurements collected before dose administration on Day 1 of each period will serve as each participant's baseline QTcF value;

- However, ***for purposes of the CSR***, within-participant, time-matched assessment of each PF-07202954 dose relative to placebo, will be reported.

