### **3.5.2. Laboratory Data**

Safety laboratory tests will be performed as described in the protocol.

To determine if there are any clinically significant laboratory abnormalities, the haematological, clinical chemistry (serum) and urinalysis safety tests will be assessed against the criteria specified in the sponsor reporting standards. Post-baseline assessments will not take into account whether each subject’s *baseline* test result is within or outside the laboratory reference range for the particular laboratory parameter.

***Baseline is defined*** as the time-matched data obtained while on placebo [Part 1], 0H assessment on Day 1 [Part 2], ***or*** closest to 0H assessment prior to dosing on Day 1 in ***each*** Period [Part 3]. Results from only the planned study visits will be considered for baseline assessment.

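### The only visible Part 1 laboratory baseline is the placebo-period value, which follows active drug in 12 of 16 participants, and the kidney-injury rule does not say which baseline it uses

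*Protocol*

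**What the plan says.** Protocol Section 7.1.2 calls for a retest when SCr rises by at least 0.3 mg/dL and SCysC by at least 30% relative to the participant's "own baseline measurement should trigger another assessment of SCr and SCysC as soon as practically feasible". Later steps in the section, on withholding dosing and on nephrology evaluation, also rest on change from baseline. The section neither defines that baseline nor cross-refers to a definition.

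The note to protocol Table 2 defines the Part 1 baseline for every non-PK endpoint "as the time-matched data obtained while on placebo [Part 1], 0H assessment on Day 1 or 0-12H or 0-24H assessment", unless the SAP specifies otherwise. For laboratory data the SAP does not depart from this: Section 3.5.2 defines baseline "as the time-matched data obtained while on placebo [Part 1], 0H assessment on Day 1 [Part 2". It adds: "Results from only the planned study visits will be considered for baseline assessment". SAP 6.6.2 points back to that definition.

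QTcF is handled differently. Protocol Section 8.2.3 sets a pre-dose reference for the conduct of Part 1 ("the average of the triplicate ECG measurements collected before dose administration on Day 1 of each period will serve as each"); the time-matched placebo comparison is kept for the CSR. No such split is given for laboratory tests.

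On design, Section 4.2.2 gives the allocation: "6 participants are planned to receive PF-07202954 and 2 participants are planned to receive placebo with all participants at the end of Part 1". Everyone is thus planned to finish with one placebo dose and as many as three active ones. Table 5 places placebo in Period 1, 2, 3 or 4, with two participants per sequence. Section 6.3.1 keeps investigators blinded to each participant's "assigned study intervention throughout the course of the study".

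**The concern.** A baseline for a safety rule should exist before the dose whose effect is being assessed, and the person applying the rule should be able to see it. A placebo-period value in a placebo-inserted crossover meets neither condition for many dosings. It may lie in the future, and the blinded investigator does not know which period it was.

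The reporting issue is separate. If an active dose caused a lasting renal change, a placebo-period value taken afterwards contains that change. Subtracting it removes the effect from the change-from-baseline summary.

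Decreased renal function is the first risk in protocol Table 1, and Section 7.1.2 is one of its named mitigations. Rat renal findings set the AUC24 limits in Section 4.3.2. SAP 7.2 would use Part 1 safety data, analysed by the SAP's methods, in any interim decision on higher Part 2 exposure.

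**Working it through.** **Inputs.** From Table 5: 2 cohorts, 4 sequences per cohort, 2 participants per sequence, 4 periods. In each cohort the four sequences have placebo in Periods 1, 2, 3 and 4 respectively.

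**Reproducing the plan's figures.** Participants: 2 × 4 × 2 = 16. In each period, 3 of the 4 sequences in a cohort are on active drug: 3 × 2 = 6 active and 2 placebo. Both match the protocol.

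**Active dosings.** 16 participants × 3 active doses = 48, if all four periods run.

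**Active dosings before the participant's own placebo period.** A sequence with placebo in Period k has k − 1 earlier active doses. The total is (0 + 1 + 2 + 3) × 2 participants × 2 cohorts = 24, and 24/48 = 50%. By period, in each cohort:

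| Period | Active dosings | No placebo value yet |
|---|---|---|
| 1 | 6 | 6 |
| 2 | 6 | 4 |
| 3 | 6 | 2 |
| 4 | 6 | 0 |

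The gap is complete at each cohort's first dose and gone by Period 4.

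**Participants whose placebo value follows active drug.** 3 of 4 sequences: 3 × 2 × 2 = 12 of 16 (75%). For 4 of them it follows three active doses.

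**Sensitivity.** If only Periods 1 to 3 run, there are 12 × 3 = 36 active dosings. Those without a placebo value at the time number 12 + 8 + 4 = 24, or 67%. The 4 participants in sequences 4 and 8 never have one.

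**Discontinuation.** Under Section 7.1, a participant whose dosing is definitively stopped does not remain in the study for further evaluation. Anyone stopped before placebo therefore never has the defined baseline, including anyone stopped for a renal signal. SAP 3.5.2 limits baseline to planned visits, so an unscheduled result cannot stand in.

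**How subtraction works.** Let b be the pre-drug SCr, and suppose an active dose in Period 1 produces a lasting rise d, with placebo in Period 2.
- Against the placebo baseline, the Period 1 change is (b + d) − (b + d) = 0.
- Against Period 1 Day -1, it is (b + d) − b = d.

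With d = 0.3 mg/dL, the Section 7.1.2 threshold, the first calculation shows nothing and the second meets the creatinine criterion.

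**Choice among pre-dose values.** As an assumed illustration, let SCr rise 0.2 mg/dL in each of two active periods without recovery. Against Period 1 Day -1 the second-period change is 0.4; against Period 2 Day -1 it is 0.2. The 0.3 threshold lies between them, so the designation matters even if a pre-dose value is intended.

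**Drug carry-over.** Doses are at least 10 days apart and the predicted half-life is about 8 h (Section 4.2.2): 10 × 24 / 8 = 30 half-lives. Residual drug is not a plausible cause; only a lasting effect would shift the placebo value.

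**The case against.** The strongest reply is that Section 7.1.2 never equates its baseline with the placebo value. The placebo definition sits in an endpoint-table note and in the SAP, so it can be read as a reporting convention. Section 7.1.2 is a bedside rule, and its singular measurement fits a pre-dose sample well. Elsewhere the documents use baseline in the ordinary pre-dose sense, as in the pregnancy-testing section and SAP 3.4. SoA Table A schedules laboratory tests on Day -1 of each period, with results reviewed before dosing. On that reading, 0 of 48 dosings lack a reference value. This stands. A reader might infer that the renal trigger cannot be computed for half the active dosings, but the documents support that only if the defined placebo baseline is the one meant.

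A reader might also infer that escalation decisions lack a renal comparison. They do not: Section 4.2.2 pools placebo data across participants for that purpose, the reviewing sponsor staff are unblinded, and the Section 6.6.1 stopping criteria include clinically significant laboratory abnormalities without tying them to the placebo baseline.

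Nor do the documents support saying that the reporting conceals renal toxicity. SAP 3.5.2 assesses abnormalities whether or not the baseline result was in range, and SAP 6.6.2 lists laboratory data as well as summarising them.

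Two further points stand. Day -1 of Periods 2 to 4 also follows active drug for most participants, so a per-period pre-dose baseline could absorb a lasting change too. And the SAP's additional safety endpoints are redacted, so how the kidney biomarkers are handled there cannot be seen; the point concerns standard laboratory data.

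What the reply does not supply is the missing designation. Screening, Period 1 Day -1 and current-period Day -1 all remain candidates, and the protocol made this choice for QTcF but not for laboratory tests.

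**Conclusion.** The concern holds in two parts. For conduct, the reference for Section 7.1.2 is unspecified. If the documents' defined baseline applies, 24 of 48 active dosings have no reference value when the rule must be used, and the blinded investigator could not identify that value once it existed. If a pre-dose value applies, the data are there and only the designation is missing.

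For reporting, the stated baseline follows active drug in 12 of 16 participants, is absent for anyone discontinued before placebo, and can absorb a lasting renal change. Absolute values and abnormality flags limit the harm.

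The counts assume that Table 5 runs as planned through four periods without replacement. The reporting point assumes that change-from-baseline laboratory tables are produced under the sponsor's standards, as SAP 6.6.2 implies by naming a baseline, and that a renal effect could outlast the interval between doses.

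**What to change.** Reconcile the protocol Table 2 note, protocol Section 7.1.2 and SAP 3.5.2. They should name the laboratory baseline that applies during conduct, make sure it is available to the blinded investigator when Section 7.1.2 is applied, and state separately which baseline applies in the CSR. Section 8.2.3 shows how the protocol already separates the two for QTcF.

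In SAP 3.5.2 and 6.6.2, add a Part 1 summary of SCr, SCysC, eGFR, UACR and UPCR as change from the Period 1 Day -1 sample, the only scheduled Day -1 sample that is pre-drug for everyone. Keep the time-matched active-versus-placebo comparison as a separate summary; it remains a sound use of the crossover.

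The cost is one sentence in each document and one extra table. No new samples are needed: SoA Table A already schedules Day -1 laboratory tests, UACR and UPCR, and Section 4.2.3 places SCysC in the standard safety laboratory tests (taken here to include the Part 1 Day -1 panel).

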7.2. Participant Discontinuation/Withdrawal from the Study

A participant may withdraw from the study at any time at his/her own request. Reasons for discontinuation from the study include the following:

- Refused further follow-up;
- Lost to follow-up;

- Death;
- Study terminated by sponsor;
- Discretion of the investigator or sponsor for safety or behavioral reasons, or the inability of the participant to comply with the protocol-required schedule of study visits or procedures at a given study site.

At the time of discontinuing from the study, if possible, an early discontinuation visit should be conducted. See the [SoA-Table A](#), [SoA-Table B](#), and [SoA-Table D](#) for assessments to be collected at the time of study discontinuation and follow-up and for any further evaluations that need to be completed. The early discontinuation visit applies only to participants who are enrolled/randomized, *and* received at least 1 dose of the study intervention, and then are prematurely withdrawn from the study. Participants should be questioned regarding their reason for withdrawal. The participant will be permanently discontinued both from the study intervention and from the study at that time.

If a participant withdraws from the study, he/she may request destruction of any remaining samples taken and not tested, and the investigator must document any such requests in the site study records and notify the sponsor accordingly.

If the participant withdraws from the study and also withdraws consent (see [Section 7.2.1](#)) for disclosure of future information, no further evaluations should be performed and no additional data should be collected. The sponsor may retain and continue to use any data collected before such withdrawal of consent.

Lack of completion of all or any of the withdrawal/early termination procedures will not be viewed as protocol deviations so long as the participant's safety was preserved.

7.2.1. Withdrawal of Consent

Participants who request to discontinue receipt of study intervention will remain in the study and must continue to be followed for protocol-specified follow-up procedures. The only exception to this is when a participant specifically withdraws consent for any further contact with him or her or persons previously authorized by the participant to provide this information. Participants should notify the investigator in writing of the decision to withdraw consent from future follow-up, whenever possible. The withdrawal of consent should be explained in detail in the medical records by the investigator, as to whether the withdrawal is only from further receipt of study intervention or also from study procedures and/or posttreatment study follow-up and entered on the appropriate CRF page. In the event that vital status (whether the participant is alive or dead) is being measured, publicly available information should be used to determine vital status only as appropriately directed in accordance with local law.

